3.1 Primary Objective

Our primary objective is to identify the t-PBM irradiance dose (50, 300, or ≥ 700 mW/cm 2) with the largest impact on PFC CBF in MDD.

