3.5 Study Endpoints

3.5.1 Primary Study Endpoints

The primary endpoint will be t-PBM effects on BOLD signal.

The specificity of t-PBM effects on BOLD signal increases will be assessed by testing three irradiance doses covering a wide range (50, 300 and ≥ 700 mW/cm 2) versus sham. If a reliable effect on BOLD (compared to sham, the BOLD increase at the optimal dose will have an effect size of Cohen's $d \geq 0.5$) is seen with PBM, the study validate BOLD fMRI as a robust biomarker of target engagement for t-PBM and act as a "go" signal. In contrast, if none of the t-PBM doses yield reliable BOLD increases, this will fail the putative mechanism (*no go*).

Rationale for the effect size (E.S.) threshold: We have previously observed large effect size changes in BOLD (Cohen's $d=0.6$) after a single administration of t-PBM (at 318 mW/cm 2)¹⁰³. In our clinical pilot study, significant, large effect size improvements in depressive symptoms were reported in MDD after 8 weeks (Cohen's $d=1.5$, $n=21$)³⁵. Given these preliminary results, we will use as threshold for the Go/No-Go decision an effect of t-PBM on BOLD at one dose (but not all doses, vs. sham) of magnitude Cohen's $d > 0.5$ (at least medium size).

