9.3 Description of Statistical Methods

9.3.1 General Approach

Before any statistical techniques are applied, the distribution of all variables will be investigated using descriptive statistics and outliers will be examined. Where necessary, non-parametric statistical methods will be used rather than relying on distributional assumptions. Since the main goal of the study is to obtain evidence about the mechanism of action, the feasibility of implementation, and the potential for efficacy of novel treatment strategies that, if warranted, will be tested in future confirmatory studies, the emphasis of the statistical analysis will be on estimation (with effect sizes and confidence intervals) rather than on hypothesis testing. Where formal hypothesis testing is employed, significance will be judged at 5% level, two-sided.

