9.3.2 Analysis of the Primary Efficacy Endpoint(s)

For each subject at each t-PBM dose (including sham) we will obtain the BOLD signal change measured in left and right dorsolateral prefrontal cortical regions of interest. These measures will be modeled as a function of dose (considered a categorical variable with 4 levels) using mixed effects models¹¹⁷, including random subject intercepts to account for the potentially correlated measures on the same subject. Since the doses will be presented to subjects in a random order, the initial model will also include order of the dose (a continuous variable) and all interactions between the dose and the order. If there is evidence for an interaction effect between dose and order, this effect will be investigated to understand how the dose effect varies as a function of week of treatment, and in such case effect size of the t-PBM doses will be estimated using only the data when the dose was given in the first week. If there is no interaction between dose and order, the order variable and the interactions will be omitted and the resulting model will be used to estimate the mean BOLD signal measures at each dose and the differences between each active t-PBM dose and sham.

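### The primary objective is to find the dose with the largest effect, but no estimate or confidence interval is planned for the difference between active doses

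*Combined protocol and SAP*

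**What the plan says.** Section 3.1 states the question: "Our primary objective is to identify the t-PBM irradiance dose" (50, 300 or at least 700 mW/cm²) "with the largest impact on PFC CBF in MDD". The Protocol Summary repeats it, and section 2.4 expects the three irradiances to show which is optimal for target engagement.

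Section 9.3.2 gives the analysis. The BOLD changes in the left and right dorsolateral prefrontal regions are "modeled as a function of dose (considered a categorical variable with 4 levels) using mixed effects models", with a random intercept for each subject. If there is no dose-by-order interaction, the order terms are dropped and the model is used to estimate a mean for each dose and "the differences between each active t-PBM dose and sham". If there is an interaction, effect sizes come only from doses given in the first week.

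Section 9.3.1 puts the emphasis on "estimation (with effect sizes and confidence intervals) rather than on hypothesis testing". Where tests are used, "significance will be judged at 5% level, two-sided". The go/no-go rule in section 3.5.1 is set against sham: a Cohen's d above 0.5 at one dose, but not at all of them. Section 9.4 expects about 24 observations per dose. It gives the precision of the optimal dose's effect size as 0.37 (80% CI) or 0.57 (95% CI).

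No section says how the optimal dose is to be chosen, and none lists a contrast between two active doses.

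**The concern.** Asking which active dose has the largest effect is a comparison among active doses. The listed outputs compare each dose with sham or describe it alone. An interval around each of two doses, or around two differences that share one sham, is not an interval for the difference between those doses. Judging separation by whether such intervals overlap is unreliable when the same subjects receive every dose.

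If the analysis stops at the listed outputs, the report can show an ordering of the three doses but not how firmly the data support it. A dose could then go into later studies as the best one when the trial cannot tell it from its neighbours, and the reader would not see this.

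**Working it through.** **Inputs.** From the documents: 30 subjects in a four-condition crossover (section 3.4); at most 20% dropout and about 24 observations per dose (section 9.4). Assumed: SD 1 for the measure at one session, a correlation ρ between sessions of the same subject from 0 to 0.7, and the true dose effects. The documents give neither ρ nor the true effects.

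**1. The plan's own precision.** 30 × 0.8 = 24. For two independent sets of 24 the half-width is z × √(2/24):
- 80%: 1.2816 × 0.2887 = 0.370
- 95%: 1.96 × 0.2887 = 0.566

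Both agree with section 9.4. They describe one difference fixed in advance, with no correlation between sessions.

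**2. Precision of an active-versus-active contrast.** Half-width = z × √(2(1 − ρ)/24).

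| ρ | Standard error | 80% half-width | 95% half-width |
|---|---|---|---|
| 0 | 0.289 | 0.37 | 0.57 |
| 0.5 | 0.204 | 0.26 | 0.40 |
| 0.7 | 0.158 | 0.20 | 0.31 |

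**3. Gaps the trial can resolve.** Power at the two-sided 5% level for a true gap between two active doses, n = 24, at ρ = 0 / 0.5 / 0.7:
- 0.2 SD: 10% / 16% / 24%
- 0.3 SD: 18% / 31% / 48%
- 0.5 SD: 41% / 69% / 89%

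**4. How often the ordering is right.** Simulation with 400,000 trials per setting, recording whether the truly best dose has the largest estimate, at ρ = 0 / 0.5 / 0.7:
- true effects 0.5, 0.3, 0.3: 63% / 74% / 83%
- true effects 0.5, 0.4, 0.3: 54% / 63% / 70%

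**5. The lead that chance alone gives.** If the three doses are equal, the expected gap between the largest and second-largest of three estimates is 3/(2√π) × √((1 − ρ)/24) = 0.846 × √((1 − ρ)/24).
- ρ = 0: 0.846 × 0.204 = 0.17 SD
- ρ = 0.5: 0.846 × 0.144 = 0.12 SD

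These leads are well inside the 95% half-widths of 0.57 and 0.40 in step 2. A reader given only the ordering could not tell such a lead from a real one.

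**6. The first-week branch.** If a dose-by-order interaction limits estimation to week one, each subject contributes one dose: 24/4 = 6 to 30/4 = 7.5 per dose. Contrasts are then between subjects. The 95% half-width is 1.96 × √(2/6) = 1.13 to 1.96 × √(2/7.5) = 1.01.

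**The case against.** **Means and intervals are planned.** A reader might infer that the analysis yields only differences from sham, or point estimates with no uncertainty. The documents do not support that: section 9.3.2 also estimates the mean at each dose, and section 9.3.1 promises confidence intervals. With complete, balanced data and random intercepts, all pairwise differences have the same standard error, so a careful reader could borrow the half-width of a sham contrast. With dropout this is only approximate, and nothing in the plan tells the analyst to do it.

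**No selection rule is written.** A reader might infer that the plan names whichever dose has the largest point estimate. That is a natural guess, but it remains an inference. What can be shown is that neither a rule nor the relevant contrast is given.

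**The decision rule is against sham.** Section 3.5.1 needs only sham contrasts, and section 9.3.2 supplies them. This stands for go/no-go, but it does not answer section 3.1. Doses at d = 0.51 and d = 0.49 fall on opposite sides of the threshold without evidence that they differ.

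**Picking the largest estimate is legitimate in phase I.** This largely stands. A correct pick in 63% or 74% of trials compares with 33% by chance, so the ordering is informative. If the doses are equal, no inferior dose is carried forward; the cost is an unsupported claim that one is better. A reader might go on to ask that a dose be called optimal only if its interval against the runner-up excludes zero. The documents do not support that either. It conflicts with the estimation emphasis, and with true effects 0.5, 0.3 and 0.3 the truly best dose would meet a 95% criterion in only 3%, 7% or 12% of trials (ρ = 0, 0.5, 0.7).

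**Zero correlation is pessimistic in a crossover.** This is also true, and section 9.4 calls its own figure a worst case. For that reason the results are shown over a range of ρ.

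**Conclusion.** The point holds. The primary objective compares active doses, and no planned output estimates the difference between them or gives its precision. A dose reported as best could reflect chance ordering, and the planned results would not show whether it does.

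The gap matters at this sample size. Under the assumed effects and correlations of 0 to 0.5, a true gap of 0.2 to 0.3 SD would be detected with 10% to 31% power, and equal doses would still show a leader by 0.12 to 0.17 SD. A higher correlation or larger gaps between doses would soften this. The missing contrasts do not depend on those assumptions. The design and the model are sound; what is missing is a reported quantity, so this should be corrected but does not undermine the trial.

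**What to change.** In section 9.3.2, add the three active-versus-active contrasts (High−Middle, High−Low, Middle−Low) from the same mixed model, with 80% and 95% confidence intervals, to the primary outputs. Report them alongside any statement of which dose has the largest estimated effect, and say so plainly when the intervals do not separate the doses. Do not make the naming of a leading dose depend on a significance-type criterion.

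Add one sentence for the interaction branch: if estimation is limited to first-week data, the contrasts are between subjects with roughly 6 to 8 per dose, and are to be reported as such.

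The cost is SAP wording and three contrasts from a model already specified, with no new data or procedures. The downside is that the trial will often have to report that its leading dose is not clearly separated from the others.

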9.3.3 Analysis of the Secondary Endpoint(s)

For each subject at each t-PBM dose (including sham) we will compute changes in brain temperature using data recorded just before and after the t-PBM administration with MR thermometry scans.(Note that for technical and logistical reasons, some subjects may not undergo MR thermometry.) We will quantify the frequency and severity of suicidal ideation experienced as well as the presence or absence of suicidal behaviors after each t-PBM session using the C-SSRS. Finally, we will use the SAFTEE, TSRQ, and adverse events logs to determine the frequency and severity of side effects and adverse events. We will model these measures as a function of dose (considered a categorical variable with 4 levels) using mixed effects models¹¹⁷, including random subject intercepts to account for the potentially correlated measures on the same subject. Since the doses will be presented to subjects in a random order, the initial models will also include order of the dose (a continuous variable) and all interactions between the dose and the order. If there is evidence for an interaction effect between dose and order, this effect will be investigated to understand how the dose effect varies as a function of week of treatment, and in such case effect size of the t-PBM doses will be estimated using only the data when the dose was given in the first week. Whenever we find there is no interaction between dose and order, the order variable and the interactions will be omitted. The resulting models will be used to estimate the mean of each measure at each dose and the differences between each active t-PBM dose and sham.

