9.3.4 Safety Analyses

See Section 9.3.3.

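### Section 9.3.3 applies the BOLD mixed model to rare yes/no safety outcomes with no link and no sparse-event method; per-dose counts with exact limits should be the main result

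*Combined protocol and SAP*

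**What the plan says.** Section 9.3.3 names four kinds of secondary measure: change in brain temperature; frequency and severity of suicidal ideation; the "presence or absence of suicidal behaviors after each t-PBM session"; and the frequency and severity of side effects and adverse events. A single instruction covers them all: "We will model these measures as a function of dose (considered a categorical variable with 4 levels) using mixed effects models". The starting model is large, since "the initial models will also include order of the dose (a continuous variable) and all interactions between the dose and the order". If an interaction is found, the "effect size of the t-PBM doses will be estimated using only the data when the dose was given in the first week". Otherwise the reduced models are to "estimate the mean of each measure at each dose and the differences between each active t-PBM dose and sham".

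Apart from the outcome, this is the procedure of Section 9.3.2 for BOLD, a continuous measure, down to the random intercepts for correlated measures within a subject. Section 9.3.3 does not say which distribution or link applies to a yes/no outcome, or what happens when a dose has few or no events. Section 9.3.4, the safety analysis section, says only "See Section 9.3.3".

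**The concern.** Comparing the safety and tolerability of the three doses is the secondary objective (Section 3.2), and suicidal behaviour and adverse events are among the secondary endpoints (Section 3.5.2). Suicidal behaviour is yes/no and probably rare here, because Section 4.1 excludes people at serious and imminent suicide risk. An individual adverse event coded as present or absent after a session can be just as sparse.

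With a few dozen sessions per dose, such outcomes will often leave a condition with no events at all. A model suited to a continuous signal then either has no finite estimate or gives intervals that do not describe a proportion. The first-week rule could also remove most of the recorded events from the dose estimates. For these outcomes the specified analysis would not show what a reader most needs: how large a risk the data still allow at each dose.

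**Working it through.** **Inputs.** 30 participants, each with one session per condition (Section 3.4). At most 20% dropout and about 24 observations per dose (Section 9.4): 30 × (1 − 0.20) = 24. The main analysis set takes anyone with at least one session (Section 9.2), so the number per dose may lie between 24 and 30. The event risk per session for suicidal behaviour is not given, so the range below is an assumption. The one rate in the documents is under 0.1% for each listed application-site event (Section 2.6.1), and that is per subject or user, not per session.

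**The plan's own precision figure.** Section 9.4 gives an effect size to within 0.37 (80% CI) or 0.57 (95% CI). The unpaired formula z × √(2/24) gives 1.282 × 0.2887 = 0.370 and 1.960 × 0.2887 = 0.566, so the figure reproduces. It is for a standardised continuous effect. No precision is stated for a binary safety outcome.

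**Chance of an empty condition.** With n sessions per dose and risk p, one dose has no events with probability (1 − p)^n. At least one of the four is empty with probability 1 − [1 − (1 − p)^n]^4, and all four are empty with probability (1 − p)^(4n), taking sessions as independent.

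| Assumed risk | At least one empty, n = 24 | At least one empty, n = 30 | All four empty, n = 24 | All four empty, n = 30 |
|---|---|---|---|---|
| 0.1% | >99.9% | >99.9% | 90.8% | 88.7% |
| 1% | 99.8% | 99.5% | 38.1% | 29.9% |
| 2% | 97.8% | 95.7% | 14.4% | 8.9% |
| 5% | 74.9% | 62.0% | 0.7% | 0.2% |
| 10% | 28.3% | 15.9% | <0.1% | <0.1% |
| 20% | 1.9% | 0.5% | <0.1% | 0.1% or less |

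If the empty condition is sham, all three contrasts with sham are affected. At n = 24 that has probability 78.6%, 29.2% and 8.0% at risks of 1%, 5% and 10%.

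**Logistic reading.** A dose with no events has no finite maximum-likelihood coefficient. The starting model has 8 fixed effects (intercept, 3 dose terms, 1 order term, 3 interactions), which makes separation more likely than an empty dose alone would. In simulated crossover data with 24 subjects (8 Latin-square sequences, subject SD of 1.5 on the logit scale assumed, 300 runs per setting), the fixed-effect design was separated in these shares of runs:

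- full dose-by-order model: 1.00, 0.99, 0.89, 0.58 and 0.12 at risks of 1%, 2%, 5%, 10% and 20%
- dose-only model: 1.00, 0.94, 0.75, 0.29 and 0.02

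The dose-only shares are close to the table, so within-subject correlation of this size changes little.

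**Linear reading.** Take an illustrative result of 0/24 on sham and 3, 2 and 1 of 24 on the active doses. An ordinary logistic fit without a random effect does not converge (coefficients near ±25, standard errors near 121,000). A linear random-intercept model does return differences of 0.125, 0.083 and 0.042. However, all three carry the same standard error, 0.068, although the rates differ, and the fit gives a boundary warning. Its 95% interval for the sham rate is −9.7% to 9.7%. The exact interval for 0/24 is 0 to 14.2%, so the linear interval includes impossible values below zero and also stops short above.

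**First-week rule.** One first session per participant leaves 24/4 = 6 to 30/4 = 7.5 sessions per dose, so three of every four sessions no longer enter the dose estimates. At least one dose is then empty with probability 99% or more at 5% risk and 91-95% at 10%.

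**What zero events allow.** The two-sided exact 95% upper limit is 1 − 0.025^(1/n): 14.2% for 0/24, 11.6% for 0/30 and 45.9% for 0/6.

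**The case against.** A reader might infer that the model cannot be estimated and that the safety comparison will yield nothing usable. The documents do not support that. Section 9.3.3 names no link; read literally as the BOLD model it is linear and returns estimates with one dose empty. Temperature, ideation severity and scale scores do not fail for this reason, and side effects occurring in about 20% or more of sessions are mostly estimable.

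A reader might also infer that the trial would declare no difference between doses. The plan states no such conclusion: Sections 9.1 and 9.3.1 put estimation with confidence intervals ahead of testing.

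Other provisions soften the problem. Section 9.3.3 first commits to quantifying these outcomes, Section 9.3.1 calls for descriptive statistics and allows non-parametric methods where needed, and Section 7.8 sends adverse-event numbers and rates by group to the DSMB. Counts would therefore survive a failed model. What does not follow is a valid analysis: Section 9.3.1 names no method or trigger, and the DSMB summaries are monitoring outputs with no stated intervals. The emphasis on estimation makes valid intervals more important.

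It is also fair to say that sample size is the real limit. At 1% risk and 24 sessions per dose there is a 38% chance of no events anywhere, and then no method can compare doses. Exact McNemar tests add little: 3 against 0 discordant pairs gives p = 2 × 0.5³ = 0.25, and significance at 5% needs at least 6 against 0 (p = 2 × 0.5⁶ = 0.031). That argues for intervals as the main result.

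**Conclusion.** The point holds for rare yes/no safety outcomes: suicidal behaviour, and individual adverse events coded as present or absent. For these, Section 9.3.3 prescribes a model that works badly under either natural reading: no finite contrast if logistic and fitted by maximum likelihood, invalid intervals if linear. An empty condition is close to certain at 1-2% risk per session, more likely than not at 5%, and a minority outcome at 10%. The first-week rule, if triggered, makes this worse and takes later events out of the dose estimates.

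The size rests on assumed event risks, on 24 to 30 sessions per dose, and on independence between sessions. The point does not extend to continuous measures or common side effects, and it has no bearing on the go/no-go decision, which Section 3.5.1 rests on BOLD.

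**What to change.** In Section 9.3.3, add a separate rule for binary safety outcomes:

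- As the main result, report for each of the four conditions, over all sessions, the number of participants with an event out of those treated, with exact (Clopper-Pearson) 95% limits. Each participant receives each condition once, so every count is a simple binomial over participants.
- Do not apply the order interaction or the first-week restriction to these outcomes.
- Exact paired comparisons with sham may be shown, labelled descriptive.
- Keep the mixed model for continuous measures such as brain temperature and scale totals.

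Section 9.3.4 can continue to refer to 9.3.3. The change is SAP wording only, with no new data, visits or participants. The downside is that the intervals are wide and not model-based.

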9.3.4 Safety Analyses

See Section 9.3.3.

9.3.5 Exploratory Analyses

We will quantify 1) depression severity using the MADRS and SDQ scores, 2) anxiety severity using the ASQ scores, and 3) perceived quality of cognition using the Neuro-QoL scores and perceived quality of life using the Q-LES_Q-SF, as assessed at the visit after each dose of t-PBM.

We will model these measures as a function of dose (considered a categorical variable with 4 levels) using mixed effects models¹¹⁷, controlling for baseline scores (from the first scan/t-PBM visit) and including random subject intercepts to account for the potentially correlated measures on the same subject. Since the doses will be presented to subjects in a random order, the initial models will also include order of the dose (a continuous variable) and all interactions between the dose and the order. If there is evidence for an interaction effect between dose and order, this effect will be investigated to understand how the dose effect varies as a function of week of treatment, and in such case effect size of the t-PBM doses will be estimated using only the data when the dose was given in the first week. Whenever we find there is no interaction between dose and order, the order variable and the interactions will be omitted. The resulting models will be used to estimate the mean of each measure at each dose and the differences between each active t-PBM dose and sham.

